13.1.1.2 Safety

Data from all subjects who receive any protocol therapy will be included in the safety analyses. Subjects who entered the study and did not receive any protocol therapy and had this confirmed, will not be evaluated for safety. Adverse events will be recorded during the entire study, weekly during the first cycle, and at the start of each cycle for subsequent cycles. Toxicity will be graded according to CTCAE v.4.0 whenever possible and reported in a descriptive way.

13.1.2 Secondary objectives and endpoints

13.1.2.1 Response

The response rate ($RR = sCR + CR + VGPR + PR$) and clinical benefit response rate ($CBRR = sCR + CR + VGPR + MR$) will be calculated for the entire study group, and for individual dose levels. Since the number of patients treated at any given dose level will be small, any report will mainly list the number of responses but may also mention the percentage of patients achieving a response.

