1.1 Overview of targeted Multiple Myeloma

Multiple myeloma, a cancer of antibody producing plasma cells, is the second most common hematologic malignancy in the United States. Based on SEER data (<http://seer.cancer.gov/statfacts/html/mulmy.html>, accessed 1/31/2013) it is estimated that 21,700 individuals were diagnosed with multiple myeloma in 2012 and that 10,710 died of the disease. Treatment has improved life expectancy with major milestones marked by the introduction of oral melphalan therapy in the late 1950s, corticosteroids prednisone or dexamethasone shortly thereafter, high dose melphalan with autologous stem cell transplant in the 1990s, and discovery of profound antimyeloma effects with the use of “new drugs” thalidomide, bortezomib, and lenalidomide around the turn of the century ¹. With improved life expectancy myeloma prevalence increases and was 71,213 in 2009 (<http://seer.cancer.gov/statfacts/html/mulmy.html>, accessed 1/31/2013). Almost all patients still experience disease progression and ultimately their disease becomes refractory to available standard therapy which includes various combinations of “new drugs” corticosteroids, and conventional chemotherapeutic agents. More recent progress includes development of carfilzomib, a second generation proteasome inhibitor which in contrast to bortezomib does not cause significant neurotoxicity and produces at least minor responses as single agent in more than one third of patients with refractory myeloma ² leading to FDA approval in 2012. Pomalidomide, an analogue of lenalidomide, in combination with dexamethasone yielded about similarly promising results in refractory myeloma ³⁻⁵ and obtained FDA approval in 2013. Despite these developments, the majority of patients with relapsed and refractory multiple myeloma do not respond to available therapy creating an unmet need for further drug development. One of the mechanisms of increasingly uncontrollable growth of cancer cells during clonal evolution as it occurs in most cancers including myeloma is epigenetic silencing of genes required for senescence, differentiation, cell death, and immune attack ⁶. The pan-histone deacetylase inhibitor panobinostat may restore intrinsic and extrinsic growth control by reactivation of respective genes and pathways through its chromatin opening effects and enhance cell death induction through inhibition of deacetylation of non-histone proteins. In a clinical study that enrolled patients who were refractory to their last bortezomib containing regimen, panobinostat added to bortezomib and dexamethasone yielded a remarkable clinical benefit response (at least minor response) of about 50% ⁷. The need for parenteral administration and neurotoxic adverse events with the use of bortezomib has led to the development of the oral proteasome inhibitor MLN9708 which has shown single agent activity in relapsed and refractory myeloma without clinically significant neuropathy ⁸⁻¹⁰. The maximal tolerated dose for MLN9708 when given as a single agent in either a twice-a-week (2mg/m²) ¹⁰ or weekly (2.97mg/m²) ⁹ administration schedule has been determined. Dosing of MLN9708 became more

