Multiple myeloma refractory to bortezomib and refractory to, relapsed after, or ineligible for IMiDs constitutes an unmet medical need with EFS and OS of 5 and 9 months, respectively, and response and clinical benefit response rates of 24 and 34%, respectively⁴⁹. A recently presented study suggests bortezomib refractoriness of multiple myeloma may be overcome by combination with panobinostat and dexamethasone. Enrolled patients were refractory to their last bortezomib containing regimen and achieved a remarkable response rate of 35% and clinical benefit response rate of 53%⁷. The oral proteasome inhibitor MLN9708 (ixazomib) appears to not only be more convenient than bortezomib but also safer; with an otherwise comparable safety profile it has not caused any severe neuropathy at doses that had single agent activity in relapsed and refractory multiple myeloma when used in a twice a week dosing schedule¹⁰ or administered weekly⁹. The MTD for MLN9708 (ixazomib), when given twice a week (day 1,4,8,11 every 21 days) to patients with relapsed or refractory multiple myeloma was established at 2mg/m², whereas weekly administration (day 1,8,15 every 28 days) was tolerated at higher doses (MTD 2.97mg/m²) in a comparable patient population^{9,10}. Another study used MLN9708 (ixazomib) in a weekly administration schedule (day 1,8,15 every 28 days) in combination with lenalidomide (25mg day 1-21 every 28 days) and dexamethasone (40mg once a week) in newly diagnosed multiple myeloma⁸. This study also found the MTD of MLN9708 (ixazomib) to be at 2.97mg/m² but recommended 2.23mg/m² for phase 2 evaluation because of improved tolerance. The most common possibly MLN9708 (ixazomib) related adverse events in these studies were thrombocytopenia, neutropenia, fatigue, and gastrointestinal adverse events including nausea and diarrhea. Gupta et al. analyzed pharmacokinetic data of the active metabolite of MLN9708 (ixazomib) from 4 trials that used either IV or PO dosing. Using a non-linear mixed effects modeling approach he found that body size affected only volume of distribution but not maximal or AUC concentrations¹¹. A decision was therefore made by the manufacturer Millennium to use flat dosing in future trials, using 2.3mg, 3mg, and 4mg tablets.

Here we aim to develop an “all oral” regimen of proteasome and histone deacetylase inhibition in combination with dexamethasone for future phase 2 study and as a platform for addition of further drugs.

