Phase II extension: Patients in phase I (median age 65, range 50-73, median previous regimens 5, range 2-10) tolerated treatment without DLT and without non-hematologic severe (grade 3 or higher) adverse event according to CTCAE vs.4.03. Three patients developed grade 3 hematologic toxicities (2 neutropenia, 1 thrombocytopenia). Worst diarrhea was grade 1 (n=6), worst nausea grade 2 (n=1) and 4 additional patients developed transient grade 1 nausea. Other possibly panobinostat or ixazomib related grade 1/2 adverse events included thrombocytopenia (n=5), neutropenia (n=3), fatigue (n=2), anemia (n=2), anorexia (n=1) and arthralgia (n=1).

Median QTcF before treatment start was 405 msec (range 378-430) and increased on average by 4.3% (maximally by 13%). One patient developed transient grade 1 QTcF prolongation to 552 msec. No other cardiac adverse events were observed. Of the 11 patients in phase I, one reached PR, two reached MR, and one had stable disease for 6 months. All patients entered the study with disease refractory to their last regimen, and in two of the responding patients (1PR, 1MR) this included a proteasome inhibitor an IMiD, and a glucocorticosteroid (carfilzomib, pomalidomide, dexamethasone in the MR patient, bortezomib, dexamethasone, lenalidomide in the MR patient). Overall, we are encouraged by activity in extensively pretreated patients and by excellent tolerance of this regimen so far. In phase II we aim to extend the study cohort by an additional 20 patients who will be treated until progression or other reasons for discontinuation arise (7.6.1) to strengthen the safety analysis and obtain a more reliable estimate of activity.

3 Study objectives

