Partial response (PR)	$\geq 50\%$ reduction of serum M protein and reduction in 24-h urinary M protein by $\geq 90\%$ or to $<200\text{mg}$ per 24 h, if the serum and urine M protein are unmeasurable, a $\geq 50\%$ decrease in the difference between involved and uninvolved sFLC levels is required in place of the M protein criteria, if the only measurable disease is in the bone marrow, a $\geq 50\%$ reduction in bone marrow plasma cells is required, provided the baseline percentage was $\geq 30\%$. In addition to the above criteria, if present at baseline, a $\geq 50\%$ reduction in the size of soft tissue plasmacytomas is required.
Minor response (MR)	$\geq 25\%$ but $\leq 49\%$ reduction of serum M protein and reduction in 24 h urine M protein by 50–89%, which still exceeds 200mg per 24 h. In addition to the above criteria,

if present at baseline, 25–49% reduction in the size of soft tissue plasmacytomas is also required. No increase in size or number of lytic bone lesions (development of compression fracture does not exclude response).

Stable disease (SD)

Not meeting criteria for sCR, CR, VGPR, PR, MR, or progressive disease (see under 5.9.1).

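### The clinical benefit response rate formula leaves out partial response, so patients with a PR are not counted as having clinical benefit

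*Combined protocol and SAP*

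**What the plan says.** Section 13.1.2.1 defines two rates in one sentence. The response rate is "RR = sCR + CR + VGPR + PR" and the clinical benefit response rate is "CBRR = sCR + CR + VGPR + MR". Both are to be calculated for the whole study group and by dose level. Reports will mainly give numbers of responses, and percentages are optional. This is the only formula for the clinical benefit response rate in the document.

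The protocol summary and Sections 3.2 and 4.2 name clinical benefit response as a secondary objective and endpoint. The summary and Section 3.2 refer to Section 8.1 for the criteria. Section 8.1 defines the individual categories but not which of them make up clinical benefit.

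The intended meaning appears in the background. Section 1.1 says that "panobinostat added to bortezomib and dexamethasone yielded a remarkable clinical benefit response (at least minor response) of about 50" percent. Section 2 reports that patients in what is evidently the same study (same reference number) "achieved a remarkable response rate of 35% and clinical benefit response rate of 53" percent.

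**The concern.** The printed sum includes the category above PR and the category below it but skips PR itself. A rate meant to capture minor response or better cannot exclude patients who did better than a minor response. As written, a patient who improves from MR to PR drops out of the numerator and returns only on reaching VGPR or better.

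The stake is the correctness of a named secondary endpoint. An analyst who follows Section 13 reports a rate that does not measure what its name says and cannot be compared with the figures in the Section 2 rationale. An analyst who sees the problem must depart from the plan to put it right.

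**Working it through.** The plan states no clinical benefit response rate for this trial, so there is no figure to reproduce. The check has four steps.

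**1. Can a PR patient enter through another term?** Section 8.1 sets MR at a 25% to 49% reduction in serum M protein, with a urine M protein "which still exceeds 200mg per 24 h". PR requires at least a 50% serum reduction, with urine M protein down by at least 90% or to below 200 mg per 24 h. The two do not overlap. The stable disease row also lists the categories separately: "Not meeting criteria for sCR, CR, VGPR, PR, MR, or progressive disease". So neither the MR term nor the VGPR term captures PR.

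**2. How do the two printed rates relate?**

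(sCR + CR + VGPR + MR) − (sCR + CR + VGPR + PR) = MR − PR

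The printed clinical benefit response rate is therefore below the response rate whenever PR patients outnumber MR patients. With PR included, the difference is simply MR, which is never negative. Both pairs of rates in Section 2 (35% and 53%; 24% and 34%) have clinical benefit above response, as this requires.

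**3. Phase I data.** Section 2 reports: "Of the 11 patients in phase I, one reached PR, two reached MR, and one had stable disease for 6 months". With no response above PR reported:

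| Rate | Count | Result |
|---|---|---|
| Response rate | 1/11 | 9.1% |
| Clinical benefit response rate as printed | 2/11 | 18.2% (exact 95% CI 2.3% to 51.8%) |
| Clinical benefit response rate with PR | (1 + 2)/11 = 3/11 | 27.3% (exact 95% CI 6.0% to 61.0%) |

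The patient with the best response of the 11 counts as a responder but not as having clinical benefit. Here the printed rate still exceeds the response rate, because MR (2) outnumbers PR (1).

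Each PR patient omitted lowers the rate by 1/11 = 9.1 points in phase I, 1/20 = 5.0 points in phase II and 1/31 = 3.2 points in the full group.

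**4. Illustration at the rates cited in Section 2.** Assume a response rate of 35% and a true clinical benefit response rate of 53%, so MR = 53 − 35 = 18%. Let s be the share of responders whose best response is PR. The documents do not give s, so the whole range is shown:

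printed rate = 53 − 35s

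| s | Printed rate |
|---|---|
| 0 | 53% |
| 0.5 | 35.5% |
| 18/35 = 0.514 | 35%, equal to the response rate |
| 1 | 18% |

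In whole patients at N = 31, those rates correspond to about 11 responders and 5 MR. With PR included the rate is 16/31 = 51.6%. As printed it runs from 16/31 = 51.6% (no PR) down to 5/31 = 16.1% (all 11 are PR). It falls below the response rate of 11/31 = 35.5% once 6 or more responders are PR.

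**The case against.** The strongest reply is that this is a dropped term with little practical effect. No test, sample size, stopping rule or dose decision uses the rate. Reports will mainly list counts, and the phase I summary already lists PR and MR separately, so a reader can rebuild the right figure. That stands, and it limits the seriousness. It does not make the formula right, and nothing in Section 13.1.2.1 requires a count for every category.

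A second reply is that the gloss in Section 1.1 describes a cited study, not this trial's endpoint. That is true, and Section 8.1 supplies no composite definition. But nothing in the document supports excluding PR, and including both neighbouring categories without it is incoherent whatever the gloss says. The phrase "two of the responding patients (1PR, 1MR") in Section 2 shows PR and MR patients grouped as responders, but it is weak support: it does not mention clinical benefit, and the text that follows it labels both patients MR.

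A third reply is that the plan does not say best response, so a patient with a confirmed MR who later reaches PR might still count as having achieved MR. This does not rescue the formula. Adding categories gives a valid rate only if each patient is counted once, at best response; otherwise a patient passing through VGPR to CR is counted twice. Even on that reading, anyone who reaches PR without a confirmed MR is lost.

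Two limits on the size are fair. The plan calls for rates overall and by dose level, so of the denominators above only 31 is a planned one. The illustration borrows another study's rates, with an unknown PR share.

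**Conclusion.** The concern holds. The formula in Section 13.1.2.1 is wrong as written: it omits PR from a rate meant to count minor response or better, and Section 8.1 leaves PR patients no other way in. On the phase I data the printed rate is 18.2% instead of 27.3%, a shortfall of one patient in 11. In the full group the shortfall is 3.2 points per PR patient, and the printed rate falls below the response rate if PR patients outnumber MR patients.

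These figures assume that each patient is counted once, at best response. The 53%-to-18% range also assumes the cited study's rates. The omission is probably a slip, and its effect is confined to a descriptive secondary endpoint. It should be corrected, but it does not threaten the trial's main conclusions.

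**What to change.** In Section 13.1.2.1, change the definition to CBRR = sCR + CR + VGPR + PR + MR, which is RR + MR. This is a one-term text correction. It needs no additional patients, visits or data.

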Phase I: Patients will remain on study for six 28-day cycles or until criteria for discontinuation (7.6.1) are met, whichever comes earlier. Decisions on subsequent maintenance therapy will at the discretion of the treating physician but if the patient's myeloma is controlled (at least in stable disease) panobinostat, dexamethasone, and ixazomib may be continued and will be provided free of charge to the patient. This protocol may be amended to include a formal maintenance phase and/or a phase II portion after review of safety and preliminary efficacy data and approval by Novartis, Millennium, and the sponsor institution (Cleveland Clinic).

Phase II: Patients will receive therapy according to DL2 and will remain on study until criteria for discontinuation (7.6.1) are met.

Efficacy Data Collected

The following evaluations will be conducted to assess the efficacy of this regimen:

Response will be assessed according to international uniform response criteria and clinical benefit response according to modified EBMT response criteria (8.1), using myeloma panels obtained at the beginning of each cycle that include SPEP, 24 h UPEP, serum and urine IFEs, and serum free light chains. In addition, a baseline bone marrow exam and skeletal survey will be obtained and repeated as clinically indicated, including repeat bone marrow exam for confirmation of complete remission (see also Section 8 schedule of assessments).

Pharmacokinetic/Pharmacodynamic/Pharmacogenomic/Correlative Studies Collected

None.

Safety Data Collected

The following evaluations will be conducted to assess the safety of this regimen:

- Dose limiting toxicity will be evaluated after the first cycle for patients in phase I
- Toxicity will be evaluated according to CTCAE version 4.0, weekly during the first cycle and whenever the dose of a drug is increased, then at the start of each subsequent

cycle

Statistical Procedures

Due to low patient numbers and short study duration results will only be described. Appropriate statistical analysis will be added if the study is extended into a phase II evaluation.

Phase II: Kaplan-Meier survival and progression-free survival estimates will be calculated.

Table of contents

PROTOCOL SUMMARY	3
Table of contents	5
List of abbreviations	8
1 Introduction	11
1.1 Overview of targeted Multiple Myeloma	11
1.2 Overview of Panobinostat.....	12
1.2.1 Anticancer activity of DAC inhibitors	12
1.2.2 Panobinostat (LBH589)	13

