13.1.2.2 PFS and OS

Progression-free survival will be measured from study entry to progression or death of any cause, whichever comes first. Overall survival for all will be measured from study entry to death from any cause. Due to small sample size and limit of treatment duration to six months only observed PFS and OS will be reported for patients participating in phase I. For patients who enter on phase II the Kaplan-Meier method will be used to estimate PFS and OS.

14 Procedures and instructions

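### Phase II was added partly to estimate activity more reliably, but Section 13.1.2.1 still reports response as counts with an optional percentage and no confidence interval

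*Combined protocol and SAP*

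**What the plan says.** Section 13.1.2.1 is the only text on the analysis of response. It defines a response rate (RR) and a clinical benefit response rate (CBRR), and says that they "will be calculated for the entire study group, and for individual dose levels". It then sets the reporting rule: "any report will mainly list the number of responses but may also mention the percentage of patients achieving a response". The reason it gives is that few patients are expected at each dose level. It mentions no confidence interval, confidence level or standard error, and none is given for response elsewhere in the document.

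The Protocol Summary, under Statistical Procedures, says: "Appropriate statistical analysis will be added if the study is extended into a phase II evaluation". The next line is what was added: "Phase II: Kaplan-Meier survival and progression-free survival estimates will be calculated". Section 13.1.2.2 matches it: "For patients who enter on phase II the Kaplan-Meier method will be used to estimate PFS and OS".

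Section 2 (Phase II extension) says that the 20 further patients are meant "to strengthen the safety analysis and obtain a more reliable estimate of activity". Section 5.1 places all 20 at DL2.

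**The concern.** The counts rule fits a small dose-escalation study. Its stated reason, few patients at each dose level, no longer describes DL2, which receives all 20 phase II patients on top of those treated there in phase I. Section 13.1.2.2 was updated to separate phase I reporting from phase II estimation. Section 13.1.2.1 was not.

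At stake is how the activity result will be read. Section 2 quotes an RR of 24% and a CBRR of 34% from a historical series, and 35% and 53% for panobinostat with bortezomib and dexamethasone. A reader given only a count or a percentage is likely to set it beside those figures without seeing how wide the uncertainty is. An aim stated as reliability of an estimate calls for some measure of how reliable the estimate is.

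**Working it through.** **Planning figure.** The Protocol Summary gives 11 + 20 = 31 patients, and the sum agrees. The document gives no target rate, power, confidence level or interval width from which the 20 could be reproduced, so there is no planned precision to check.

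**Inputs.**
- Phase II: n = 20, all at DL2 (Section 5.1).
- Phase I activity: 1 PR and 2 MR among 11 patients (Section 2).
- Rates quoted in Section 2: RR 24% and CBRR 34% (historical); RR 35% and CBRR 53% (panobinostat, bortezomib, dexamethasone).
- Assumptions of this review: a 95% level, and illustrative phase II counts.

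**Size of the DL2 group (inferred, not stated).** Section 5.1 puts the first three patients at DL1 and requires at least 6 at a level before it is called tolerated. With 11 phase I patients, DL2 therefore held between 6 and 11 − 3 = 8 of them. Adding 20 gives 26 to 28.

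**Formula.** For x responders of n, the exact (Clopper-Pearson) 95% limits are
- lower = the 0.025 quantile of Beta(x, n − x + 1);
- upper = the 0.975 quantile of Beta(x + 1, n − x).

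| Group | x/n | Estimate | Exact 95% CI |
|---|---|---|---|
| Phase I, RR (observed) | 1/11 | 9.1% | 0.2% to 41.3% |
| Phase I, at least MR (observed) | 3/11 | 27.3% | 6.0% to 61.0% |
| Phase II, RR (illustrative) | 5/20 | 25.0% | 8.7% to 49.1% |
| Phase II, RR (illustrative) | 7/20 | 35.0% | 15.4% to 59.2% |
| Phase II, CBRR (illustrative) | 11/20 | 55.0% | 31.5% to 76.9% |
| All DL2, lower inferred n | 9/26 | 34.6% | 17.2% to 55.7% |
| All DL2, upper inferred n | 9/28 | 32.1% | 15.9% to 52.4% |
| Whole study (illustrative) | 11/31 | 35.5% | 19.2% to 54.6% |

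At 7/20 the half-width is (59.2 − 15.4)/2 = 21.9 points, and the interval contains 24%. At 11/20 the CBRR interval contains both 34% and 53%. With all 31 patients the half-width at 11/31 is still (54.6 − 19.2)/2 = 17.7 points.

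**How often 20 patients would separate the quoted rates.**
- RR: the lower limit is 23.1% at 9/20 and 27.2% at 10/20, so at least 10 responders are needed for the interval to lie above 24%. If the true RR is 35%, P(X ≥ 10), X ~ Binomial(20, 0.35), is 12%.
- CBRR: the lower limit is 31.5% at 11/20 and 36.1% at 12/20, so at least 12 are needed to lie above 34%. If the true CBRR is 53%, P(X ≥ 12), X ~ Binomial(20, 0.53), is 35%.

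The plan makes no such comparison. These figures only show how little a percentage from 20 patients can say about those rates.

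**The CBRR formula.** Section 13.1.2.1 sums sCR, CR, VGPR and MR, and leaves out PR. On the phase I data that formula counts 2/11 (18.2%), while the number with at least a minor response is 1 + 2 = 3, or 3/11 (27.3%). An interval built on the formula as written would describe the wrong count.

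**The case against.** The strongest case against the point is that it is minor. The primary objective is tolerability and safety. Response is secondary, with no hypothesis, threshold or go/no-go rule, so no planned decision depends on an interval. Anyone given a count and a denominator can compute one. The example counts are illustrative, and an interval around an observed 35% is bound to contain 35%. All of this stands. It fixes the size of the point but does not remove it: the plan names no denominator for response (the all-treated set in Section 13.1.1.2 is for safety), and an exact interval is descriptive and needs no hypothesis.

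A reader might infer four stronger things, and the documents do not support them.
- That the main result mixes the 3 mg and 4 mg levels. The same sentence also provides rates by dose level, and no estimate is named as the main one.
- That the promise of phase II statistics was ignored. It was kept in part, through Kaplan-Meier for progression-free and overall survival. The gap is confined to response.
- That activity is the sole purpose of phase II. Section 2 gives two purposes, with safety first.
- That the pooled phase I and II patients at DL2 are plainly the right main group. Pooling adds patients, but phase I had a six-cycle limit (Section 5.2) and its own off-study rules for delays (Sections 7.4 and 7.6.1). The phase I responses were already known and were cited as encouragement for the extension. The 20 phase II patients are the cleaner main group, and the pool is better used as support.

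**Conclusion.** The point holds as a reporting gap. The rule in Section 13.1.2.1 rests on a reason that no longer applies to DL2, and response is the one efficacy measure for which phase II brought no estimation method. At n = 20 the missing information is large: about 22 points either side of an observed 35%, enough to include the 24% historical rate. The result rests on a 95% level and illustrative counts, both assumed here. The DL2 total of 26 to 28 is inferred from Section 5.1 and should be labelled as such. The primary endpoint, the sample size and the error rates are not affected.

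**What to change.** In Section 13.1.2.1, replace the sentence on listing counts with:

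> RR and CBRR will be reported with number, denominator (all treated patients), percentage and exact Clopper-Pearson 95% CI for the phase II patients (n=20, DL2). The same will be given as supportive results for all patients treated at DL2 and for the entire study group, with DL1 listed separately.

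In the same edit:
- add PR to the CBRR formula, before any interval is computed;
- state the actual number treated at DL2 in phase I, so that the DL2 total need not be inferred;
- bring Statistical Procedures in the Protocol Summary into line, replacing the promise of future analysis with what is now planned for response, progression-free survival and overall survival.

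The cost is a few lines of text. No further patients, visits or data are needed, and the calculation is trivial.
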